#### **5.2.7. Cumulative Incidence Plots**

Cumulative incidence plots will be produced based on the time to the event of interest (starting from the time of start of dosing on Day 1; finishing at Week 22) for the treatment groups separately, on the same plot. This will be based on plotting the cumulative incidence function (with no competing risks), which will be presented as a percentage on the y-axis. Participants who discontinue from the study or from study intervention will be censored at the associated discontinuation date (i.e. date of death, study withdrawal, lost-to-follow-up, or last dose of IP +31 days). Number of participants at risk at each timepoint will be included in the plot.

Example SAS code is provided in Appendix 4.

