Any planned or potential discontinuation of study drug should be discussed with the TIMI Hotline (available 24/7). Note that discontinuation of study intervention does not represent withdrawal from the study. If it is confirmed that the participant will permanently discontinue study intervention following discussion with the TIMI Hotline, an Early Termination visit should be performed, which should include assessments of patient-reported outcomes, physical activity (6MWT), and laboratory assessments. In addition, a follow-up visit (F/U1) should be completed approximately 28 days and another follow-up visit (F/U2) should be completed ideally no more than 94 days for the Main Cohort (Cohort A)/Cohort C/Cohort D, and ideally no more than 75 calendar days for the open-label, PK cohort (Cohort B), after discontinuing study intervention primarily for the purpose of assessing resolution of any treatment-related AEs. See the [SoA](#) for data to be collected at the time of discontinuation of study intervention and follow-up for any further evaluations that need to be completed.

Again, it is important to first contact the TIMI Hotline before classifying a subject as ‘Discontinued from Study Intervention’ and completing an Early Termination visit.

In the event of discontinuation of study intervention, it must be documented on the appropriate CRF/in the medical records whether the participant is discontinuing further receipt of study intervention or also from study procedures, posttreatment study follow-up, and/or future collection of additional information.

Follow-Up:

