### 3.3.14. Clinical outcomes (Cohorts A, C and D)

Both investigator-reported and adjudicated events will be recorded.

#### 3.3.14.1. Hierarchical composite endpoint of time to cardiovascular death, number of worsening HF events (hospitalization for HF, or urgent HF visit), time to first worsening HF event and change from baseline in KCCQ-23 CSS at Week 22

The time (days) to cardiovascular death will be calculated for each participant.

The number of hospitalizations for HF and the number of urgent HF visits, over the 22 weeks, will be calculated for each participant. The total number of these worsening heart failure events will also be calculated for each participant, as well as the total number divided by the number of days of study participation (up to Week 22), where 'number of days of study participation' = time from randomization to Week 22, or to time lost-to-follow-up, withdrawal from study, or death. This total will then be multiplied by 154 days in order to provide a 22-week estimate. Similarly, the total number of combined cardiovascular deaths and worsening heart failure events will be calculated.

The composite HF outcome (cardiovascular death, hospitalization for HF or urgent HF visits) will be determined for each participant as well as each individual component as a first event.

The time (days) to first hospitalization for HF and the time (days) to first urgent HF visit will be calculated for each participant. The time to the first of these worsening HF events (hospitalization for HF or urgent HF visit) will also be calculated for each participant.

The change from baseline in KCCQ-23 CSS at Week 22 will be calculated (see Section 3.1.1).

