**4. ANALYSIS SETS (POPULATIONS FOR ANALYSIS)**

Participant Analysis Set	Description
Enrolled/Randomly assigned to study intervention	"Enrolled" means a participant's agreement to participate in a clinical study following completion of the informed consent process and randomization. A participant will be considered enrolled if the informed consent is not withdrawn prior to participating in any study activity after screening. Potential participants who are screened for the purpose of determining eligibility for the study, but do not participate in the study, are not considered enrolled, unless otherwise specified by the protocol.
Evaluable	All participants randomly assigned to study intervention and who take at least 1 dose of study intervention (not including the open-label placebo administered in screening), for the given part of the study (Main Cohort [Cohort A], open-label, PK cohort [Cohort B], Cohort C or Cohort D). Participants will be analyzed according to the randomized intervention.
Safety Analysis Set	All participants randomly assigned to study intervention and who take at least 1 dose of study intervention (not including

	
the open-label placebo administered in screening), for the given part of the study (Main Cohort [Cohort A], open-label, PK cohort [Cohort B], Cohort C or Cohort D). Participants will be analyzed according to the product they actually received. This will be the study intervention received by the participant for the majority of the timepoints during the study (not including the open-label placebo administered in screening). If a participant receives an equal number of different doses, then the lowest of those doses will be used. If a participant receives an equal number of placebo and a given dose of ponesegromab, the ponesegromab dose will be used.

--	--

Defined Analysis Set	Description
Censored	All evaluable participants. For participants who discontinue study intervention or receive a prohibited procedure, all observations post-discontinuation (i.e. last dose of IP +31 days), or post-procedure, will be censored and treated as missing data. For participants who miss a dose, or receive an incomplete dose, all observations post-missed/incomplete dose will be censored. For participants who resume dosing, their subsequent data may be included in the analysis following a review of their compliance prior to database lock.

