### 6.3. Other Endpoint(s)

Unless otherwise stated these analyses will be performed on the censored analysis sets, as defined in Section 4, using efficacy approaches 1, 3 and 4, as described in Section 5.2, unless otherwise stated.

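### The tertiary CV-death and worsening-HF analyses inherit on-drug censoring that conflicts with the SAP's own outcome definitions, and no all-events version is planned

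*SAP*

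**What the plan says.** SAP 6.3 sets the default for every tertiary endpoint: "Unless otherwise stated these analyses will be performed on the censored analysis sets, as defined in Section 4". Section 6.3.14, which holds the win ratio, the logistic model, the Cox models and the cumulative incidence plot, specifies adjudicated events but no other analysis set.

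The Censored set in SAP Section 4 has two relevant rules. After stopping drug or a procedure: "all observations post-discontinuation (i.e. last dose of IP +31 days), or post-procedure, will be censored and treated as missing data". After a dosing lapse: "For participants who miss a dose, or receive an incomplete dose, all observations post-missed/incomplete dose will be censored". SAP 4.2 lets data back in once complete dosing resumes, subject to review before database lock.

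SAP 5.2.7 writes the 31-day rule out for the incidence plot: "Participants who discontinue from the study or from study intervention will be censored at the associated discontinuation date". SAP 5.2.6 leaves values missing through censoring unimputed in the logistic model. SAP 5.2.8 (Cox) and 5.2.9 (win ratio) give no censoring date.

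The endpoint definitions read differently. SAP 3.3.14.1 sets the participation period for worsening-HF counts as "time from randomization to Week 22, or to time lost-to-follow-up, withdrawal from study, or death". SAP 3.3.14.3 does likewise for days alive and out of hospital, and it counts any death before Week 22. Protocol 7.1 says that stopping drug is not withdrawal from the study. Protocol 8.2.5 collects deaths and worsening-HF events during the trial and sends them to blinded adjudication.

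On event rates, SAP 3.3.14.1 divides each participant's count by days of participation and adds: "This total will then be multiplied by 154 days in order to provide a 22-week estimate".

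**The concern.** Under the default, the trial collects and adjudicates events that its hazard ratios, odds ratios and win ratio then leave out. In heart failure the participants who leave treatment may well be those who are worsening. Protocol 7.1 requires stopping for heart transplantation or mechanical circulatory support, and prohibited procedures also trigger censoring. If leaving treatment tracks prognosis, the participants still counted do not represent those removed, and the result is no longer a comparison of the randomized groups over 22 weeks.

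The Complete set keeps all post-discontinuation data, but the SAP applies it only to the primary KCCQ-23 CSS endpoint (6.1.1.2). Nothing planned would show whether the censoring mattered for the clinical outcomes.

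The consequence reaches past the final report. SAP 7.2.1 runs the interim on the relevant Section 4 set, and 7.2.1.1 derives a predictive probability of end-of-study success from the composite HF logistic model. SAP 7.1 allows interim results to inform futility or early-success decisions.

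**Working it through.** **Inputs.** Protocol 9.5: 15% discontinuation; 190 per arm on 300 mg and placebo. Protocol schedule of activities: doses on Days 1, 29, 57, 85, 113 and 141. SAP 3.3.14.3: Week 22 is Day 155, a 154-day window. The documents give no event rate, event count or power for these outcomes, so event risks and post-stopping hazards below are assumptions.

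**1. The plan's own figure.** 190 × 0.85 = 161.5, against 161 evaluable per arm stated. It reproduces.

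**2. Follow-up lost per stopper** = 155 − (last dose day + 31).

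| Last dose | Censored on | Days lost | Share of 154 |
|---|---|---|---|
| 1 (Day 1) | Day 32 | 123 | 80% |
| 2 (Day 29) | Day 60 | 95 | 62% |
| 3 (Day 57) | Day 88 | 67 | 44% |
| 4 (Day 85) | Day 116 | 39 | 25% |
| 5 (Day 113) | Day 144 | 11 | 7% |

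**3. Person-time lost at 15% stopping.**
- Spread evenly over doses 1 to 5: (123 + 95 + 67 + 39 + 11)/5 = 67 days; 0.15 × 67/154 = 6.5%. The extremes are 1.1% (all stop after dose 5) and 12.0% (all stop after dose 1).
- Spread continuously over Days 0 to 141: (123²/2)/141 = 53.7 days; 0.15 × 53.7/154 = 5.2%.

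**4. Events lost.**
- Continuous version, with L = 0.15 × 53.7 = 8.05 days and hazard multiple m after stopping: m × L/(154 − L + m × L). This gives 5.2% at m = 1 and 22% at m = 5.
- Dose-day version: daily hazards, on-drug 22-week risk of 5 to 15%, and hazard raised from 28 days after the last dose. Losses are 6.2 to 6.4% at m = 1, 11.2 to 11.8% at m = 2 and 18.5 to 20.4% at m = 4. At 10% risk that is about 2.4, 4.6 and 8.7 events per 380 participants.

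**5. Effect on a comparison.** Take equal on-drug hazards, 10% on-drug risk, and stopping of 20% in one arm and 10% in the other (all assumed).
- m = 4: the all-follow-up risk ratio is 1.10; the censored hazard ratio is 1.01.
- m = 1: both are 1.00, and only precision is lost.
- Censored event counts over full-participation denominators: ratio about 0.96 at m = 1, with no true difference. This is what mixing the 6.3 default with the 3.3.14.1 denominator would produce.

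**6. Win ratio.** When neither member of a pair had a CV death, the example code in SAP Appendix 4 awards that tier to the longer time. The SAP does not define this time for survivors. If it is the censoring time, being censored earlier loses the pair at the top tier.

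**7. Scaled rates.** A CV death on Day 3 with no other event gives 1/3 × 154 = 51 events for that participant, which adds 51.3/190 = 0.27 to the arm mean. Pooled by arm, the same death is one event over the arm's total person-days.

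**8. Follow-up after stopping.** Protocol 7.1 places F/U2 "ideally no more than 94 days for the Main Cohort (Cohort A)/Cohort C/Cohort D" after stopping. 155 − 94 = 61, so for a participant who stops before about Day 61 that visit may fall before Day 155.

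**The case against.** The strongest reply is that an on-drug estimand may be intended. SAP 2.2.5 allows tertiary endpoints to use estimands similar to the hypothetical primary one, these outcomes are exploratory, and the primary analysis does not depend on them. That stands as a reason to keep an on-drug analysis. It does not explain why 3.3.14 defines follow-up by participation, or why no all-events companion exists.

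Several stronger readings are tempting, and the documents do not support them:
- **That the SAP states the 31-day rule for every model.** The 5.2.7 sentence governs the plot. The Cox, logistic and win-ratio analyses inherit the rule from the section default. For counts and days alive out of hospital, the SAP contradicts itself rather than clearly censoring.
- **That an HF admission which interrupts dosing is lost.** An admission that precedes the missed dose is counted, so time to first event and the yes/no composite already have it. A later CV death is at risk of being dropped only if complete dosing has not resumed or the data are not reinstated.
- **That the comparisons are invalid or could hide harm.** Bias needs a changed hazard after stopping and, in the example above, unequal stopping between arms. The documents establish neither. Safety tables use the Safety set with a 365-day window after the last dose, deaths are tabulated as a reason for discontinuation, and an unblinded E-DMC monitors safety.
- **That early stoppers leave follow-up near Day 61.** The 94-day limit is only an ideal, and Protocol 7.2.1 keeps participants who stop drug in the study.

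Two further cautions are fair. The 15% may include deaths and withdrawals, whose follow-up no rule can recover. The scaled rates are descriptive and accompanied by medians and raw totals; 6.3.14.4 names the division by days but not the multiplication; and a Day 3 death is an extreme chosen to show the artefact.

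**Conclusion.** The concern holds as a conflict in the SAP with a plausible bias, not as a demonstrated one. Read as written, 6.3.14 drops adjudicated events that the trial collects and that 3.3.14 counts, and no planned analysis restores them to the Cox, logistic, incidence or win-ratio results.

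The person-time loss of 5 to 6.5% rests on 15% all being drug discontinuation with follow-up continuing, and on an even spread of stopping times. The event loss rests on an assumed hazard multiple after stopping; no point between the unchanged hazard and the 4-to-5-fold case can be preferred from the documents. Losses after procedures and missed doses come on top and cannot be sized. The distortion of per-participant scaled rates is real but confined to descriptive output.

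This should be changed before the clinical outcomes are analysed, including the composite at the interim. It is not a threat to the primary conclusion.

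**What to change.** State one rule across SAP 3.3.14, 5.2.6 to 5.2.9 and 6.3.14:
- **Main analysis:** all adjudicated events from randomization to Day 155 in all evaluable participants, regardless of study-drug status. Censor only at study withdrawal, loss to follow-up or non-CV death. In the incidence plot, treat non-CV death as a competing event; 5.2.7 currently assumes none.
- **Sensitivity analysis:** the version censored 31 days after the last dose, labelled on-treatment.
- **Win ratio:** define the survivor's time variable so that earlier censoring alone cannot decide the CV-death tier.
- **Interim:** apply the same follow-up rule to the composite HF analysis in 7.2.1.1, which uses investigator-reported events.
- **Rates:** report total events / total person-days × 154 by arm, in place of the mean of per-participant scaled rates.
- **Ascertainment:** confirm that vital status and HF events are obtained to Day 155 for participants who stop drug early.

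The cost is SAP wording, one extra set of outputs on events already collected and adjudicated, and, where F/U2 falls short, a contact at Day 155 for the few early stoppers.

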#### **5.2.8. Cox Proportional Hazards Model**

The Cox proportional hazards model will include treatment as a fixed term in the model. Additional terms may be fitted in the model (eg, cohort, baseline LVEF, log GDF-15 concentration from SV1, baseline log NT-proBNP, baseline KCCQ-23 CSS), as appropriate. Hazard ratios versus placebo (and 90% CIs) will be provided. No adjustments will be made for multiplicity.

Standard SAS output will be provided to support the statistical summary table for the analysis model.

Example SAS code and further details of the statistical methodology is provided in Appendix 4.

### 5.2.9. Win-Ratio Approach

The unmatched win-ratio approach is a method for analysing hierarchical composite endpoints, applying the following principle to all possible patient pairs between the treatment group and the control group (i.e. each patient in the treatment group is compared with every patient in the control group): -

- For any pair, the result for the most important outcome determines the “winner” (e.g. the one who dies later, if time to death is the most important outcome). If the winner cannot be determined, the second-most important outcome is considered, and so forth until the winner can be determined; otherwise the pair is tied.
- The win ratio is the ratio of winners to losers for the treatment group.

The unmatched win-ratio approach will only include the 300 mg ponesimab and placebo treatment groups. The number of ‘winners’ and the number of ‘losers’ for ponesimab 300 mg versus placebo will be provided, as well as the win-ratio (and 90% CI) versus placebo.

Example SAS code is provided in Appendix 4.

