Approximately 416 participants will be enrolled into the Main Cohort (Cohort A) and randomized to one of 3 doses of ponsegromab (100 mg [n=18], 200 mg [n=18], or 300 mg [n=190]) or to matched placebo (n=190). Participant randomization will be stratified based on CCI [REDACTED] KCCQ-23 CSS: <45 or ≥45. Approximately 195 additional participants may be enrolled into optional Cohort C and randomized in a 2:1 ratio to either 100 mg ponsegromab (n~130) or to matched placebo (n~65). The additional participants in optional Cohort C will allow for a more comprehensive evaluation of the safety and efficacy of the ponsegromab 100 mg dose level compared to placebo. For each of these cohorts, blinded study drug will be administered SC Q4W for a total of 6 doses during the 22-week treatment period.

The primary endpoint for the study is the change from baseline at Week 22 in KCCQ-23 CSS, an HRQL PRO instrument. CCI [REDACTED]

Approximately 100 participants (maximum of approximately 150) who meet all eligibility criteria for Cohorts A and C, except the requirement for serum GDF-15 concentration CCI pg/mL, may be enrolled into the optional Cohort D and randomized in a 1:1 ratio to either 300 mg ponsegromab (n~50) or to matched placebo (n~50), administered SC Q4W for a total of 6 doses during the 22-week treatment period. Participant randomization in Cohort D will be stratified by KCCQ-23 CSS: <45 or ≥45. The purpose of this optional cohort is for a supportive assessment of efficacy and safety endpoints across the spectrum of GDF-15 concentrations in participants with HF.

This study will use an unblinded E-DMC to monitor the safety of participants and an unblinded IRC to monitor the efficacy and safety of participants. A blinded Steering Committee will monitor the proportion of study participants with various NYHA classes, left ventricular ejection fractions, GDF-15 concentrations, KCCQ-23 CSS scores, and the relative proportions qualifying under the cachexia, fatigue, and functional impairment criteria and may cap 1 or more to ensure a broad population.

This study will also use a separate blinded adjudication committee consisting of independent external experts who will be responsible for adjudication of all deaths and investigator-reported HF hospitalizations and urgent HF visits.

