4. STUDY DESIGN

4.1. Overall Design

This is a Phase 2, parallel-group, randomized, double-blind, placebo-controlled study to evaluate the effect of ponsegromab on HRQL, physical activity, and circulating biomarkers in adult participants with HF and elevated circulating GDF-15.

For the Main Cohort (Cohort A), Cohort C, and Cohort D, following the 56-day screening period to confirm eligibility, the study will include a 22-week treatment period (from Day 1 to Week 20, and Week 22 for primary endpoint collection), and a 10-week follow-up period for a total study duration of 32 weeks not including the screening period.

Approximately 416 participants will be enrolled into the Main Cohort (Cohort A) and randomized to one of 3 doses of ponsegromab (100 mg [n=18], 200 mg [n=18], or 300 mg [n=190]) or to matched placebo (n=190). Approximately 195 additional participants may be enrolled into optional Cohort C and randomized in a 2:1 ratio to either 100 mg ponsegromab (n~130) or to matched placebo (n~65). The participants in optional Cohort C will allow for a more comprehensive evaluation of the safety and efficacy of the ponsegromab 100 mg dose level compared to placebo. For each of these cohorts, blinded study drug will be administered SC Q4W for a total of 6 doses during the 22-week treatment period.

Participant randomization will be stratified based on CCI

CCI

KCCQ-23 CSS: <45 or ≥45.

The primary endpoint for the study is the change from baseline at Week 22 in KCCQ-23 CSS, an HRQL PRO instrument.

Approximately 100 participants (maximum of approximately 150) who meet all eligibility criteria for Cohorts A and C, except the requirement for serum GDF-15 concentration CCI pg/mL, may be enrolled into the optional Cohort D and randomized in a 1:1 ratio to either 300 mg ponsegromab (n~50) or to matched placebo (n~50), administered SC Q4W for a total

of 6 doses during the 22-week treatment period. Participant randomization in Cohort D will be stratified by KCCQ-23 CSS: <45 or ≥ 45 . The purpose of this optional cohort is for a supportive assessment of efficacy and safety endpoints across the spectrum of GDF-15 concentrations in participants with HF.

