## 5.2. General Methods

*Following PCD, the data will be analyzed and reported in a CSR. The results for the open-label, PK cohort (Cohort B) may be reported in a separate CSR.*

*For safety analyses and PK/PD/immunogenicity analyses, the Main Cohort (Cohort A) and Cohort C will be reported combined, with data from the same treatment group combined across cohorts; the open-label, PK cohort (Cohort B) will be reported separately; Cohort D will be reported separately.*

Efficacy analyses will be produced using 4 different approaches:

1. Main Cohort (Cohort A) only: The main efficacy analyses for the 300 mg ponesegromab treatment group will be performed using data from the Main Cohort (Cohort A) only; statistical models will include data from the 300 mg ponesegromab treatment group and placebo only. Summaries will include data from all treatment groups.
2. The open-label, PK cohort (Cohort B) only: The open-label, PK cohort (Cohort B) will be presented separately from the Main Cohort (Cohort A), Cohort C and Cohort D.
3. Main Cohort (Cohort A) and Cohort C combined: The main statistical analyses for the 100 mg and 200 mg ponesegromab treatment groups will be performed using combined data from the Main Cohort (Cohort A) and Cohort C; statistical models will include data from all three ponesegromab treatment groups and placebo, with these analyses also providing sensitivity analyses for the 300 mg ponesegromab treatment group. Summaries will include data from all treatment groups. Data from the same treatment group will be combined across cohorts, and cohort will be added as a term in the statistical models.
4. Main Cohort (Cohort A) and Cohort D combined: These analyses will provide sensitivity analyses for the 300 mg ponesegromab treatment group, in participants with any serum GDF-15 concentration. Both summaries and statistical models will include data from the 300 mg ponesegromab treatment group and placebo only. Data from the same treatment group will be combined across cohorts, and cohort will be added as a term in the statistical models.

The analyses related to the primary, secondary and exploratory endpoints will be based on the appropriate population for analysis (see Section 4).

Unless otherwise stated, all summaries and plots will be presented by treatment group. The following treatment group labels (or similar) will be used:

DMB02-GSOP-RF02 7.0 Statistical Analysis Plan Template 31-Jan-2022

PFIZER CONFIDENTIAL

TMF Doc ID: 98.03

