**6.3.14. Clinical outcomes (Cohorts A, C and D)**

The following sections are applied to adjudicated clinical outcome events. Summaries and analyses will use efficacy approaches 1, 3 and 4 for all endpoints, as described in Section 5.2.

**6.3.14.1. Hierarchical composite endpoint of time to cardiovascular death, number of worsening HF events (hospitalization for HF, or urgent HF visit), time to first worsening HF event and change from baseline in KCCQ-23 CSS at Week 22**

The hierarchical composite will be analyzed using the unmatched, win-ratio approach, as described in Section 5.2.9.

Additionally, the number of participants with the composite HF outcome (cardiovascular death, hospitalization for HF or urgent HF visits), and the number of participants with each individual component as their first event, will be summarized descriptively by treatment group, as described in Section 5.2.2. The presentation will also include the total number of combined cardiovascular deaths and worsening HF events (HF hospitalizations and urgent HF visits), including the total number of each component, summarized descriptively by treatment group, as described in Section 5.2.2.

The number of participants with the composite HF outcome (cardiovascular death, hospitalization for HF or urgent HF visits) over 22 weeks will also be analyzed using a logistic regression model (as described in Section 5.2.6), without any multiple imputation.

**6.3.14.2. Time to first occurrence of the clinical composite of cardiovascular death, hospitalization for HF, or urgent HF visit**

Time to first occurrence of the clinical composite (and the individual components: HF hospitalization, urgent HF visit, worsening HF event, cardiovascular death) will be summarized descriptively by treatment group, as described in Section 5.2.1.

A cumulative incidence plot, as described in Section 5.2.7, will be produced for the time to first occurrence of the clinical composite.

Time to first occurrence of the clinical composite (and the individual components: HF hospitalization, urgent HF visit, worsening HF event, cardiovascular death) will be analyzed using a Cox proportional hazards model, as described in Section 5.2.8. Note that for efficacy approaches 3 and 4, cohort will be included as a term in the statistical model.

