Example SAS code for Cox Proportional Hazards Model:

To obtain the hazard ratio and 90% CI use SAS proc phreg:

```
proc phreg data=dataset;
  class trt (ref='Placebo') / param=ref order=internal;
  model time*censor(1)= cohort LVEF lgGDF15 lgBNP KCCQ trt / ties=Breslow
    risklimits alpha=0.1;
  hazardratio 'Comparisons vs Placebo' trt / diff=ref alpha=0.1;
run;
```

NOTE: cohort will be included only when data from more than one cohort are included).

Example SAS code for Win-Ratio:

```
* alpha for 100*(1-alpha)% confidence interval;
%let alpha = 0.10;

* number of patients (sample size) in Treatment group;
%let n_trt = 10;

* number of patients (sample size) in Control group;
%let n_con = 10;

data trt;
  set HFdata;
  if treatment = "Ponsegromab";
  rename subject_ID = subid_trt cardio_death=death_trt t_death=t1_trt
    HF_event=HF_trt t_HF=t2_trt CFB_KCCQ=KCCQ_trt;
run;
```

```

data ctrl;
  set HFdata;
  if treatment = "Placebo";
  rename subject_ID = subid_ctrl treatment=control
          cardio_death=death_ctrl t_death=t1_ctrl
          HF_event=HF_ctrl t_HF=t2_ctrl CFB_KCCQ=KCCQ_ctrl;
run;

**** Determine winner in each pair of treatment vs placebo patients ****;

proc sql;
  create table pwdata as
  select a.*, b.*
  from trt as a, ctrl as b
  order by subid_trt, subid_ctrl;
quit;

data compare;
  set pwdata;
  by subid_trt subid_ctrl;

  * win=0: winner not determined, win=1: winner determined or tie;
  win = 0;

  * wincat: winning category;
  * wincat='a','c','e','g' if Control patient won per Endpoint time to
  cardiovascular death, number of worsening HF events, time to 1st
  worsening HF event, CFB in KCCQ-23 at week 22, respectively;
  * wincat='b','d','f','h' if Treatment patient won per Endpoint time to
  cardiovascular death, number of worsening HF events, time to 1st
  worsening HF event, CFB in KCCQ-23 at week 22, respectively;
  * wincat='t' if a pair of patients are tied;
  wincat = ' ';

  if death_trt = 1 then do;
    if death_ctrl = 0 then wincat='a';
    * Control patient won per time to cardiovascular death;
    else if death_ctrl = 1 and t1_trt < t1_ctrl then wincat = 'a';
    * Control patient won per time to cardiovascular death;
    else if death_ctrl = 1 and t1_trt > t1_ctrl then wincat = 'b';
    * Treatment patient won per time to cardiovascular death;
    else if HF_trt > HF_ctrl then wincat = 'c';
    * Control patient won per number of worsening HF events;
    else if HF_trt < HF_ctrl then wincat = 'd';

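### Under approach 3 the 300 mg win ratio pools Cohort C placebo patients without cohort stratification, so about a quarter of its pairs are non-randomised and could bias an exploratory sensitivity result

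*SAP*

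**What the plan says.** SAP 6.3.14 covers all clinical outcomes: "Summaries and analyses will use efficacy approaches 1, 3 and 4 for all endpoints, as described in Section 5.2". Section 6.3.14.1 sends the hierarchical composite (CV death, number of worsening HF events, time to first such event, KCCQ-23 CSS change) to the win ratio of Section 5.2.9. There, "The unmatched win-ratio approach will only include the 300 mg ponesimab and placebo treatment groups", and "each patient in the treatment group is compared with every patient in the control group". The planned output is winners, losers, the win ratio and a 90% CI.

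In SAP 5.2, approach 1 (Cohort A only) is the main analysis for 300 mg. Approach 3 (A and C combined) is a sensitivity analysis for that dose, with this rule: "Data from the same treatment group will be combined across cohorts, and cohort will be added as a term in the statistical models".

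Protocol 4.1 gives the allocation. Cohort A has "300 mg [n=190]) or to matched placebo (n=190". Cohort C is "randomized in a 2:1 ratio to either 100 mg ponsegromab (n~130) or to matched placebo (n~65". It has no 300 mg arm.

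SAP 6.3.14.2 (Cox model) repeats that cohort is included under approaches 3 and 4; 6.3.14.1 does not. In Appendix 4 the MMRM, imputation, logistic, ANCOVA and Cox examples carry a note on cohort. The win-ratio example has none: it cross-joins all treated and placebo records without a cohort key.

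**The concern.** When approach 3 is fitted as a model, the cohort term separates the A-to-C difference from the 300 mg effect. A win ratio is a count over pairs and has no term to carry that adjustment. Followed as written, the analysis compares Cohort A patients on 300 mg with a mixture of Cohort A and Cohort C placebo, so an A-to-C difference enters the estimate as if it were a drug effect.

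The documents give reasons why the cohorts might differ:

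- **Calendar time.** Cohort C came in with Amendment 2, dated 18 Jul 2024 in SAP Table 1. The interim efficacy population of Cohort A was randomised by 07 May 2024, for an interim set at about 70% of randomised Cohort A participants reaching Week 22 or discontinuing (SAP 7.2.1). Much of Cohort A therefore predates Cohort C.
- **Case mix.** The Steering Committee may cap patient categories during enrolment (Protocol 10.1.5.1).
- **Expectation.** The chance of active drug is 2:1 in Cohort C. Placebo is volume-matched to the dose arm, and 178 of the 190 Cohort A placebo patients are matched to 300 mg. The last tier of the composite is patient-reported.

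At stake is the purpose of the sensitivity analysis. If approaches 1 and 3 disagreed on the win ratio, the disagreement could not be attributed to cohort, chance or drug.

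**Working it through.** **Inputs.** Cohort A: 190 on 300 mg, 190 placebo. Cohort C: 65 placebo, 0 on 300 mg. Cohort D: 50 and 50. Discontinuation 15% (Protocol 9.5).

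**The plan's own figures.** 190 × 0.85 = 161.5 (stated 161). 65 × 0.85 = 55.25 (stated 55). 416 + 20 + 195 + 150 = 781 (stated 781). All reproduce. The plan gives no power or error figure for the win ratio.

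**Pairs under approach 3.**

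- All pairs: 190 × (190 + 65) = 48,450.
- Within Cohort A, randomised: 190 × 190 = 36,100, or 74.5%.
- Cohort A 300 mg against Cohort C placebo: 190 × 65 = 12,350, or 25.5%.
- On completers the cross-cohort share is 55/(55 + 161) = 25.5%.

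**Null win ratio, KCCQ tier alone.** Let d be the Cohort C minus Cohort A mean KCCQ change. With no drug effect, p = [190 × 0.5 + 65 × Φ(−d/(SD√2))]/255 and the win ratio is p/(1 − p). For d = −5 points and an assumed SD of 18: Φ(0.196) = 0.578, p = (95 + 37.6)/255 = 0.520, win ratio 1.083. Over SD 15–20, Cohort C being 2 to 5 points worse gives 1.03–1.10; 2 to 5 points better gives 0.97–0.91.

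**Full hierarchy, no drug effect.** The simulations decide pairs as Section 5.2.9 describes, use the Appendix 4 variance, and count results beyond z = 1.645. Gaps, SDs, event rates and the missing-KCCQ share are assumptions.

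Set 1: CV death 4%, any worsening-HF event 10%, KCCQ missing 15%. There were 1,500 trials for the first two rows and 5,000 for the others.

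| Cohort C relative to A | False favourable |
|---|---|
| No gap | 4.7% |
| KCCQ 0.1 SD worse | 7.4% |
| KCCQ 0.2 SD worse | 9.9% |
| KCCQ 0.25 SD worse | 10.2% |
| KCCQ 0.3 SD worse | 12.4% |
| 0.2 SD worse, HF event risk 15% | 13.5% |
| 0.3 SD worse, HF event risk 15% | 15.9% |

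Set 2: KCCQ SD 18 points, CV death 4%, 0.15 HF events per patient, KCCQ missing 15%; 1,000 trials per row (Monte Carlo SE about 0.7 points at 5%).

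| Cohort C relative to A | Win ratio | Favourable | Unfavourable |
|---|---|---|---|
| No gap | 1.00 | 5.2% | 5.5% |
| 5 points worse | 1.06 | 11.0% | 1.6% |
| 5 points better | 0.95 | 2.4% | 9.8% |
| Events higher (6%, 0.25) | 1.06 | 14.0% | 2.1% |
| Events lower (2%, 0.08) | 0.95 | 1.6% | 9.8% |
| 5 points worse and events higher | 1.11 | 21.7% | 0.9% |
| 5 points better and events lower | 0.91 | 0.4% | 20.7% |

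Cohort A pairs alone stayed at 4.6–5.2% in set 1 and 3.6–6.5% per side in set 2.

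**Within-cohort pairing.** 190 × 190 + 0 × 65 = 36,100 pairs, which is approach 1 exactly.

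**Approach 4.** All pairs: 240 × 240 = 57,600. Cross-cohort: 2 × 190 × 50 = 19,000 (33.0%). Half are A on 300 mg against D placebo and half the reverse, so a cohort gap cancels in expectation. With Cohort D shifted by 0.3 SD and given a different HF rate, the simulated win ratio was 1.00, with 4.3–4.8% rejection per side.

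**The case against.** The case for leaving the plan alone has real strength.

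**Stakes.** The composite is tertiary with no estimand. SAP 5.1 plans no formal testing outside the primary, secondary and selected exploratory efficacy endpoints, and the composite is not named as selected. Section 5.2.9 asks for an interval, not a p-value; one appears only in example code offered as a guide. The error rates above therefore describe how often the interval would mislead, not a decision rule in the plan. This stands.

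**Similarity of the cohorts.** A and C share eligibility criteria, stratification factors, visit schedule and blinded adjudication. The documents quantify no gap, and Cohort C is optional. This stands too: the bias is conditional.

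**Precision.** A reader might infer that Cohort C placebo can add only bias, or that the approach 3 result says nothing about the drug. The documents do not support either: 74.5% of the pairs are randomised. If the cohorts are exchangeable, the SE shrinks by a factor of about √[(1/190 + 1/255)/(2/190)] = 0.93; simulated, 0.130 falls to 0.121. At a 0.2 SD gap the mean squared error of the log win ratio is still slightly below approach 1 (0.0161 against 0.0169). At 0.3 SD it is higher.

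**Approach 4.** A reader might extend the criticism there because a third of its pairs cross cohorts. Cohort D is "300 mg ponsegromab (n~50) or to matched placebo (n~50" and Cohort A is also 1:1 for these arms, so cohort is balanced between arms and there is no bias to correct.

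None of this answers the central point: the plan adjusts for cohort in its pooled models, and this analysis has no means of doing so.

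**Conclusion.** The point holds as a low-severity, cheap improvement. That 25.5% of the approach 3 pairs are non-randomised follows from the text and allocation alone. The size of any bias does not: it rests on an assumed A-to-C difference. With Cohort C worse by 0.1 SD in KCCQ change, false-favourable results are about 7%; at 0.2–0.3 SD, about 10–12%. They go higher if event rates also differ, and the error reverses if Cohort C does better. With no difference, the result is unbiased and slightly more precise.

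A reader might infer that the approach 3 win ratio measures cohort plus drug instead of drug, or that it threatens the trial's conclusion on 300 mg. The first treats a partial and conditional contamination as certain. The second overlooks that the approach 1 win ratio, which is the main analysis for this dose, uses no Cohort C data.

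**What to change.** In SAP 6.3.14.1, state that the 300 mg win ratio is not run under approach 3. The alternative is to state that pairs are formed only within cohort, which makes approach 3 identical to approach 1; the Appendix 4 example would then join on cohort and compute its variance and covariance by cohort. Within-cohort pairing under approach 4 is optional. The change is best made before unblinded Cohort C results exist.

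The cost is a sentence of SAP wording and, for the second option, a few lines of code. No patients or data are affected. What is lost is one exploratory output and its possible 7% reduction in standard error if the cohorts prove exchangeable.
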